5.1.1 Investigational Drug

5.1.1.1 Pomalidomide

Pomalidomide, 4-amino-2-(2,6-dioxo-3-piperidyl)isoindoline-1'-one)-1,3-dione, belongs to the IMiDs class of compounds. The Chemical Abstract Service (CAS) registry number for CC-4047 is 19171-19-8. The chemical structure of the active pharmaceutical ingredient (API) is as follows:

Pomalidomide has an asymmetric carbon atom and can therefore exist as the optically active forms S (-) and R (+). Pomalidomide is being developed as a racemate.

5.1.1.2 CLINICAL PHARMACOLOGY

Mechanism of Action:

Pomalidomide is an IMiD analogue of thalidomide that, among other anti-tumor properties, on an equimolar basis in vitro, displays equivalent anti-angiogenic activity, about 8-fold greater activity in stimulation of apoptosis, at least 10-fold greater activity in inhibition of cellular COX-2 production and over 4,000-fold greater activity in inhibition of cellular TNF-alpha production relative to thalidomide [9,10]. Pomalidomide has also been shown to stimulate antibody-dependent cytotoxic T-cell activity (ADCC) [11].

5.1.1.3 Dose and tolerability:

Pomalidomide was safe at doses of up to 50 mg in a Phase I single dose study in normal, healthy male volunteers and up to 5 mg QOD or 2 mg QD in a Phase I multidose clinical study in subjects with relapsed or refractory multiple myeloma; DLTs seen in subjects receiving higher doses were predominantly hematopoetic (i.e., neutropenia), and lower grade, self-limited neutropenia was also seen in some of the 1 and 2 mg QD and 5 mg QOD recipients. In a multidose, Phase II clinical study of subjects with prostate cancer, 2 mg QD dosing was well tolerated and, unlike the multiple myeloma subjects who received 1 and 2 mg QD doses, only an overall shift to lower neutrophil counts was noted. No clinically relevant neutropenic AEs were observed, and no grade 3 or 4 neutropenic events occurred. It is, therefore, likely that subjects with solid tumors that do not extensively involve the bone marrow will have a higher pomalidomide MTD than subjects with hematologic malignancies.

5.1.1.4 Supplier(s)

Celgene Corporation will supply pomalidomide.

5.1.1.5 Dosage form

Pomalidomide will be supplied as 1.0 mg and 2.0 mg capsules for oral administration.

5.1.1.6 Packaging

Pomalidomide will be shipped to the pharmacy at the study site in individual bottles. Bottles will contain a sufficient number of capsules to last for one cycle of dosing. Study drug must be dispensed in the original packaging with the label clearly visible.

5.1.1.7 Labeling

Pomalidomide investigational supplies are dispensed to the subjects in individual bottles of capsules. Each bottle will identify the contents as study medication. In addition, the label will bear Celgene's name, quantity contained and the standard caution statement as follows: Caution: New drug - Limited by Federal law to investigational use. Pomalidomide should not be handled by FCBP unless wearing gloves. All bottles will contain the following warning label: "WARNING: POTENTIAL FOR HUMAN BIRTH DEFECTS."

The study drug label must be clearly visible. Additional labels must not cover the Celgene label.

5.1.1.8 Receipt of study drug

The Investigator or designee is responsible for taking an inventory of each shipment of study drug received, and comparing it with the accompanying study drug accountability form. The Investigator will verify the accuracy of the information on the form, sign and date it, retain a copy in the study file, and return a copy to Celgene or its representative.

5.1.1.9 Storage

At the study site, all investigational study drugs will be stored in a locked, safe area to prevent unauthorized access.

The study drug should be stored at room temperature away from direct sunlight and protected from excessive heat and cold.

5.1.1.10 Unused study drug supplies

Celgene will instruct the Investigator on the return or destruction of unused study drug. If any study drug is lost or damaged, its disposition should be documented in the source documents. Study drug supplies will be retained at the clinical site pending instructions for disposition by Celgene. Subjects will be instructed to return empty bottles or unused capsules.

5.1.1.11 Drug dispensing requirements

Pomalidomide (POMALYST®) will be provided to research subjects for the duration of their participation in this trial at no charge to them or their insurance providers. Pomalidomide will be provided in accordance with the Celgene Corporation's POMALYST REMSTM program. Per the standard POMALYST REMSTM program requirements, all physicians who prescribe pomalidomide for research subjects enrolled into this trial, and all research subjects enrolled into this trial, must be registered in and must comply with all requirements of the POMALYST REMSTM program.

Drug will be shipped on a per patient basis by the contract pharmacy to the clinic site for IND studies. Only enough pomalidomide for one cycle of therapy will be supplied to the patient each cycle. This is in accordance with the POMALYST REMS[™] program.

5.1.1.12 Dexamethasone (Decadron®)

We will be using the oral formulation, which is available from any pharmacy. Each tablet, for oral administration, contains 0.25 mg, 0.5 mg, 0.75 mg, 1.5 mg, 4 mg or 6 mg of dexamethasone.

Dexamethasone (Decadron) is a synthetic adrenocortical steroid and is readily absorbed from the gastrointestinal tract. Chemically, dexamethasone is 9-fluoro-11b, 17, 21-trihydroxy-16a-methyl-pregna-1, 4-diene-3, 20-dione.

5.2 Screening and Eligibility

The Investigator is responsible for keeping a record of all subjects who sign an Informed Consent Form for entry into the study. All subjects will be screened for eligibility. Screening procedures are outlined in Section 2, Schedule of Study Assessments and unless otherwise specified, must take place within 28 days prior to initiation of therapy.

Approximately 30 subjects with previously treated AL amyloidosis will be screened for enrollment and must meet the eligibility criteria below.

Pregnancy Testing

Must follow pregnancy testing requirements as outlined in the POMALYST REMS[™] program.

5.2.1 Inclusion Criteria

Subjects must meet the following inclusion/exclusion criteria to be eligible for the study.

Inclusion criteria

- 1. Understand and voluntarily sign an informed consent form.
- 2. Age ≥ 18 years at the time of signing the informed consent form.
- 3. Able to adhere to the study visit schedule and other protocol requirements.
- 4. Biopsy proven tissue amyloid deposits or positive fat aspirate
- 5. Proof of AL type (either a or b suffices)
- 6. Measurable plasma cell dyscrasia (a or b) AND c of the following required:
 - a. Monoclonal protein in the serum or urine by immunofixation electrophoresis
 - b. Plasmacytosis of bone marrow (< 30% plasma cells) with monoclonal staining for kappa or lambda light-chain isotype

- c. dFLC \geq 50 mg/L (dFLC=difference in involved and uninvolved serum free light-chain levels)
- 7. Must have received ≥ 1 prior treatment for AL amyloidosis, if it is intensive chemotherapy and an autotransplant it must be at least 3-6 months prior to enrollment on this study
- 8. Subjects must have recovered from the reversible side effects of any prior therapy; permanent and stable side effects/changes are acceptable. Prior treatment for AL amyloidosis with chemotherapy, thalidomide, lenalidomide or steroids is not an exclusion.
- 9. SWOG performance status of ≤ 2 at study entry (see Appendix 2).
- 10. Laboratory test results within these ranges:
 - d. Neutrophil $\geq 1.5 \text{ x}10\text{e}9/\text{L};$
 - e. Platelets $\geq 100 \times 10e9/L$;
 - f. Total bilirubin $\leq 1.5 \text{ mg/dL}$
 - g. AST (SGOT) and ALT (SGPT) \leq 2 x ULN
 - h. Serum creatinine $\leq 3.0 \text{ mg/dL}$
- 11. Disease free of prior malignancies for ≥ 5 years with exception of currently treated basal cell, squamous cell carcinoma of the skin, or carcinoma "in-situ" of the cervix or breast.
- 12. Females of childbearing potential (FCBP)[†] must have a negative serum or urine pregnancy test with a sensitivity of at least 50 mIU/mL within 10–14 days prior to and again within 24 hours of starting pomalidomide and must either commit to continued abstinence from heterosexual intercourse or begin TWO acceptable methods of birth control, one highly effective method and one additional effective method AT THE SAME TIME, at least 28 days before she starts taking pomalidomide. FCBP must also agree to ongoing pregnancy testing. Men must agree to use a latex condom during sexual contact with a FCBP even if they have had a vasectomy. All subjects must be counseled at a minimum of every 28 days about pregnancy precautions and risks of fetal exposure. See Appendix: 1 Risks of Fetal Exposure, Pregnancy Testing Guidelines and Acceptable Birth Control Methods, AND also Appendix 1: Education and Counseling Guidance Document.

[†] A female of childbearing potential is a sexually mature woman who: 1) has not undergone a hysterectomy or bilateral oophorectomy; or 2) has not been naturally postmenopausal for at least 24 consecutive months (i.e., has had menses at any time in the preceding 24 consecutive months).

- 13. Able to take aspirin (81 or 325 mg) daily as prophylactic anticoagulation (subjects intolerant to ASA may use warfarin or low molecular weight heparin or direct factor Xa inhibitors or newer anticoagulants, per preference of the patient and investigator).
- 14. All study participants must be registered into the mandatory POMALYST REMS[™] program, and be willing and able to comply with the requirements of the POMALYST REMS[™] program.

5.2.2 Exclusion criteria

- 1. Subjects with secondary or familial amyloidosis
- 2. Subjects with multiple myeloma (≥30% plasma cells in a bone marrow biopsy specimen or lytic bone lesions)
- 3. Cytotoxic chemotherapy or radiation therapy ≤ 4 weeks of initiation of study therapy.
- 4. Subjects with symptomatic cardiac arrhythmias or O₂-dependent restrictive cardiomyopathy
- 5. Dialysis-dependent
- 6. Subjects with untreated or uncontrolled infections.
- 7. Any serious medical condition, laboratory abnormality, or psychiatric illness that would prevent the subject from signing the informed consent form.
- 8. Pregnant or breast feeding females. (Lactating females must agree not to breast feed while taking pomalidomide).
- 9. Any condition, including the presence of laboratory abnormalities, which places the subject at unacceptable risk if he/she were to participate in the study or confounds the ability to interpret data from the study.
- 10. Use of any other experimental drug or therapy within 28 days of initiation of study therapy.
- 11. Known intolerance to steroids.
- 12. Known hypersensitivity to thalidomide or lenalidomide.

- 13. The development of erythema nodosum if characterized by a desquamating rash while taking thalidomide or similar drugs.
- 14. Concurrent use of other anti-cancer agents or treatments.
- 15. Known HIV positivity is not an exclusion, unless CD4 counts <200/mcL and/or patient has multi-drug resistant HIV infections and/or other concurrent AIDS-defining conditions. HIV b-DNA < 75 copies/mL.

5.3 Visit schedule and assessments

Screening Assessments and all on study scheduled visits and assessments are outlined in Section 2 Table of Study Assessments.

At treatment discontinuation, subjects will undergo off study evaluations per the Schedule of Assessments, Section 2. In addition, a safety assessment will be done approximately 30 days post the last dose of study drug. Follow-Up contact with the subjects should occur at a minimum of every 3 months until progression, then annually.

5.4 Drug Administration

5.4.1 Treatment assignments

The Phase I portion of the study will be aimed at determining the safety profile and the MTD of Pomalidomide. A 3+3 dose escalation scheme will be implemented. Subjects will receive escalating doses of Pomalidomide orally on D1-21 in a 28-day cycle* in the absence of disease progression or unacceptable toxicity. DLTs will be assessed in Cycle 1 only. Dose escalation of Pomalidomide will continue until MTD has been identified or a maximum planned dose (4 mg/day D1-21) is determined to be safe.

* Pomalidomide dosing for Phase I cohorts 1 and 2 given on days 1-28 of a 28-day cycle and changed to Days 1-21 of a 28 day cycle with Cohort 3.

The Phase II portion of the study will begin after determination of the MTD and evaluation of the safety profile at the MTD in at least 6 subjects. The dose for administration will be informed by the results of the Phase I portion of the study. In the Phase II, eligible subjects will receive Pomalidomide at the MTD or the maximum planned dose from D1-21.

Once the MTD is defined during Phase I, patients currently receiving treatment may discuss the option with the treating investigator to continue on their current dose, or increase to the MTD, if they have not achieved a complete response.

5.4.2 Dosing regimen

The initial planned dose of pomalidomide for investigation is 2 mg/day, orally on days 1 - 21 (28 day cycle).* Dosing will be in the evening at approximately the same time each day,

either 2 hours before or 2 hours after food ingestion. Participants will be instructed to avoid smoking, as smoking can decrease the efficacy of pomalidomide. Only enough pomalidomide for one cycle of therapy will be supplied to the subject each cycle.

* Pomalidomide dosing for Phase I cohorts 1 and 2 given on days 1-28 of a 28-day cycle and changed to Days 1-21 of a 28 day cycle with Cohort 3.

The planned dose levels of Pomalidomide are presented below in Table 15-1 table.

		Enrollment (Number of Subjects)					
Dose Group	Pomalidomide Dose (mg/dose)	Initial	Expanded at MTD ^a				
1	2	3 ^b	3				
2	3	3	3	12			
3	4	3	3				

Table 15-1 Planned Study Drug Doses

a. Twelve additional subjects are to be enrolled in an expanded cohort for analysis of efficacy and treated at the MTD for each dosing schedule.

b. If the first 2 subjects enrolled experience DLT then this cohort is closed and further subjects will be evaluated at 1mg/day dose and the cohort expanded at that dose.

The dose escalation rules will follow the standard Fibonacci method.

Dose escalation algorithm

At least 3 subjects are to be enrolled in each dose group, beginning with the 2 mg/dose. Within each dose group, 3 subjects are to complete at least 2 treatment cycles. It is noted that if the first 2 subjects in the first cohort develop DLT, then the cohort at the 1 mg/dose dose will be defined as the MTD.

Dose escalation within a cohort is not allowed.

- If after all 3 subjects complete 1 treatment cycle:
 - No subject experiences DLT, then enrollment at the next planned dose level may commence.
 - One subject experiences DLT, then 3 additional subjects are to be enrolled at the current dose level.
 - If 1 of 6 subjects experiences DLT, then enrollment at the next planned dose level may commence.
 - If 2 or more of 6 subjects experience DLT, then the previous dose is declared the MTD.

Two or more subjects experience DLT, then the previous dose is declared the MTD.

- Dose escalation continues through the 3 dose levels in order to define the MTD based on the occurrence of DLT in the first cycle. Definitions of DLT and MTD are as follows:
- DLT Based on the first cycle; toxicity considered by the investigator to be related to Pomalidomide; Grade 4 thrombocytopenia or neutropenia; ≥ Grade 3 nonhematologic toxicity
- MTD The dose level at which DLT occurs in no more than 1 of 6 subjects (ie, the dose level below that at which DLT was established).

Subjects will take aspirin 325 mg/day to prevent venous thrombosis while on pomalidomide.

A proton pump inhibitor will be used for GI prophylaxis.

Pomalidomide capsules should be swallowed whole, and should not be broken, chewed or opened. Pomalidomide should be taken without food, at least 2 hours before or 2 hours after a meal.

If a dose of pomalidomide is missed, it should be taken as soon as possible on the same day. If it is missed for the entire day, it should not be made up, rather it should be taken as usual at the next scheduled time.

Subjects who take more than the prescribed dose of pomalidomide should be instructed to seek emergency medical care if needed and contact study staff immediately.

Subjects experiencing adverse events may need study treatment modifications (See section 5.5).

5.4.3 Special Handling Instructions

Females of childbearing potential should not handle or administer pomalidomide unless they are wearing gloves.

5.4.4 Record of administration

Accurate records will be kept of all study drug administration (including dispensing and dosing) will be made in the source documents.

5.5 Dose Continuation, Modification and Interruption

Subjects will be evaluated for AEs at each visit with the NCI CTCAE v4.0 (Appendix 3: NCI CTCAE v4.0) used as a guide for the grading of severity. Refer to Sections 6.5.1, 6.5.2

_			
Poma	lida	hmide	١.
i una	nuu	Jinuc	•

and 6.5.3 for instructions on beginning a new cycle of therapy and dose-modifications during a cycle of therapy.

5.5.1 Dose-Modification Guidelines

During the study, the focus of the evaluations is on the assessment of toxicity to document the occurrence of DLT. Although DLTs may occur at any point during treatment, only DLTs occurring during Cycle 1 of treatment must influence decisions regarding doseescalation, expansion of a dose level, or evaluation of intermediate dose levels. However, DLTs occurring in later cycles may be taken into consideration for dose-escalation decisions, at the discretion of the investigators. Unless a DLT is documented to have occurred, no dose modification is allowed during Cycle 1.

In the event that a patient experiences DLT during Cycle 1, treatment should be held and the event will be counted toward the assessment of MTD for the given cohort. Patients experiencing DLTs in Cycle 1 may be restarted following recovery from toxicity at the discretion of the investigator according to the guidelines provided in Section 5.5.2. If a decision is made to restart study therapy following a DLT, the pomalidomide dose must be reduced 1 dose level. The patient will be evaluated weekly for possible toxicities that may have occurred after the previous dose(s). If multiple toxicities are noted, the dose adjustments and/or delays should be made according to the most severe toxicity guidelines.

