5.5.2 Dose-Reduction Steps

Dose-reduction steps are below:

Table 1: Pomalidomide Dose Reduction Steps for Phase I and II				
Starting Dose	MTD (as determined in Phase I portion) mg daily on Days 1-28 every 28 days			
Dose Level – 1	Decrease by 1 mg daily from MTD on Days 1-21 every 28 days*			
Dose Level – 2	Decrease by 2 mg daily from MTD on Days 1-21 every 28 days*			
Dose Level – 3	Decrease by 3 mg daily from MTD on Days 1-21 every 28 days*			

* Pomalidomide dosing for Phase I cohorts 1 and 2 given on days 1-28 of a 28-day cycle and changed to Days 1-21 of a 28 day cycle with Cohort 3.

Table 2: DEXAMETHASONE Dose Reduction Steps for Phase I and II		
Starting Dose 20 mg QD once weekly every 28 days		
Dose Level –1	10 mg QD once weekly every 28 days	
Dose Level –2	4 mg QD once weekly every 28 days	

Pomalidomide	Page 27 of 66 Protocol:

Dosing will be adjusted as needed by study investigators as outlined in the tables in Section 5.5.3. If dexamethasone is permanently discontinued, the patient will continue with single agent Pomalidomide.

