5.5.3 Instructions for initiation of a New Cycle

A new course of treatment may begin on the scheduled Day 1 of a new cycle if:

- The ANC is \geq **1,000**/mm³;
- The platelet count is \geq 50,000/mm³;
- Any pomalidomide-related rash, neuropathy or cardiac event that may have occurred has resolved to ≤ grade 1 severity;
- Any other pomalidomide-related adverse events that may have occurred have resolved to \leq grade 2 severity.

If these conditions are not met on Day 1 of a new cycle, the subject will be evaluated weekly and a new cycle of treatment will not be initiated until the toxicity has resolved as described above. If pomalidomide dosing was held during the previous cycle and was restarted with a one-level dose reduction without requiring an interruption for the remainder of the cycle, then that reduced dose level will be initiated on Day 1 of the new cycle. If **pomalidomide dosing was omitted due to an attributable toxicity (see table 3) for the remainder of the previous cycle or if the new cycle is delayed due to attributable toxicity newly encountered on the scheduled Day 1, then the new cycle will be started with a one-level dose reduction of pomalidomide. If pomalidomide is permanently discontinued, the subject will be removed from study. If dexamethasone is permanently discontinued, the subject may continue on single-agent pomalidomide.**

5.5.4 Instructions for dose modifications or interruptions during a cycle.

Table 3: Pomalidomide Dose Modifications for toxicities attributable to Pomalidomide			
NCI CTCAE Toxicity Grade	Onset Day 2-14 of Cycle	Onset ≥ Day 15 of Cycle	
Grade 3 neutropenia associated with fever (temperature ≥ 38.5º C) or Grade 4 neutropenia ¥	 Hold (interrupt) pomalidomide dose. Follow CBC weekly. If neutropenia has resolved to ≤ grade 2 prior to Day 21, restart pomalidomide at next lower dose level and continue the cycle. If neutropenia is the only toxicity for which a dose reduction is required. G-CSF may be used and the pomalidomide dose maintained ¥ 	 Omit pomalidomide for remainder of cycle See Instructions for Initiation of a New Cycle and reduce the dose of pomalidomide by 1 dose level. If neutropenia is the only toxicity for which a dose reduction is required. G-CSF may be used and the pomalidomide dose maintained for the next cycle at the investigators discretion.¥ 	

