Thrombocytopenia ≥Grade 3 (platelet count < 50,000/mm³)	 Hold (interrupt) pomalidomide dose. Follow CBC weekly Hold prophylactic anticoagulation for thrombocytopenia (grade 3 or 4) or bleeding. Prophylactic anticoagulation can be resumed when platelet count ≥50k (≤2 grade) and no sign of bleeding. If thrombocytopenia resolves to ≤ grade 2 prior to Day 21, restart pomalidomide at next lower dose level and continue the cycle. 	 Omit pomalidomide for remainder of cycle See Instructions for Initiation of a New Cycle and reduce the dose of pomalidomide by 1 dose level. Hold prophylactic anticoagulation for thrombocytopenia (grade 3 or 4) or bleeding. Prophylactic anticoagulation can be resumed when platelet count ≥50k (≤2 grade) and no sign of bleeding. 	
Non-blistering rash Grade 3 Grade 4	 If Grade 3, hold (interrupt) pomalidomide dose. Follow weekly. If the toxicity resolves to ≤ grade 1 prior to Day 21, restart pomalidomide at next lower dose level and continue the cycle. 	 Omit pomalidomide for remainder of cycle. See Instructions for Initiation of a New Cycle and reduce the dose of pomalidomide by 1 dose level. Discontinue pomalidomide. Remove subject from study. 	
	Discontinue pomalidomide. Remove subject from study.		
Desquamating (blistering) rash- any Grade	Discontinue pomalidomide. Remove subject from study.	Discontinue pomalidomide. Remove subject from study.	
Neuropathy Grade 3	 Hold (interrupt) pomalidomide dose. Follow at least weekly. If the toxicity resolves to ≤ grade 1 prior to Day 21, restart pomalidomide at next lower dose level and continue the cycle. 	 Omit pomalidomide for the remainder of the cycle. See Instructions for Initiation of a New Cycle and reduce the dose of pomalidomide by 1 dose level. 	
Grade 4	 Discontinue pomalidomide. Remove subject from study. 	Discontinue pomalidomide. Remove subject from study.	

Pomalidomide

Table 3: Pomalidomide Dose Modifications for toxicities attributable to Pomalidomide			
NCI CTCAE Toxicity Grade	Onset Day 2-14 of Cycle	Onset ≥ Day 15 of Cycle	
Venous thrombosis/embolism ≥ Grade 3	 Hold (interrupt) pomalidomide and start anticoagulation; restart pomalidomide at investigator's discretion (maintain dose level). 	Omit pomalidomide for remainder of cycle. See Anticoagulation Consideration (Section 5.6.1.2)	

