other non-hematologic toxicity ≥ Grade 3	 Hold (interrupt) pomalidomide dose. Follow at least weekly. If the toxicity resolves to ≤ grade 2 prior to Day 21, restart pomalidomide at next lower dose level and continue the cycle. 	 Omit pomalidomide for remainder of cycle. See Instructions for Initiation of a New Cycle and reduce the dose of pomalidomide by 1 dose level. 	
Hyperthyroidism or hypothyroidism ≥ Grade 2	 Omit pomalidomide for remainder of cycle, evaluate etiology, and initiate appropriate therapy. If the toxicity resolves to ≤ grade 1 prior to Day 21, restart pomalidomide at next lower dose level and continue the cycle. 	 Omit pomalidomide for remainder of cycle, evaluate etiology, and initiate appropriate therapy. See Instructions for Initiation of a New Cycle and reduce the dose of pomalidomide by 1 dose level. 	
Any attributable or non- attributable hospitalization or toxicity grade < 2	 Pomalidomide may be held or continued at the discretion of the treating investigator. Once resumed, maintain dose level. 	 Pomalidomide may be held or continued at the discretion of the treating investigator. If held, see Instructions for Initiation of a New Cycle and maintain dose level. 	

¥ As stated in the table, pomalidomide should be held for occurrence of grade 3 neutropenia with fever or grade 4 neutropenia attributable to Pomalidomide. Follow CBC weekly.

If neutropenia has resolved to \leq grade 2 prior to Day 21, restart pomalidomide at next lower dose level and continue the cycle. If neutropenia is the only toxicity for which a dose reduction is required, G-CSF may be used and the pomalidomide dose can be maintained. In case of second occurrences of Grade 4 neutropenia or Grade 3 neutropenia with fever in the setting of GCSF, pomalidomide will be held and if neutropenia has resolved to \leq grade 2 prior to Day 21, restart pomalidomide at next lower dose level with addition of G-CSF

Table 4: Non-hematological toxicity attributable to dexamethasone			
	Grade 1-2	Grade 3-4	
Dyspepsia / Gl	Start H2-blocker or Proton Pump Inhibitor if not already on one of these.	Hold dexamethasone and start H2- blocker or Proton Pump Inhibitor if not already on one of these. Once toxicity has decreased to Grade 0-2, resume Dex at one dosing level lower with continued H2B or PPI. If Grade 3-4 toxicity persists for more than 14	

Dose Modifications for Dexamethasone

		days,endoscopy or other UGI
		evaluation is encouraged.

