Edema	May add diuretic	Decrease dex by one dosing level, and
		add diuretics
Confusion/Mood Alteration	For Grade 2, decrease	Hold dex until severity decreases to
	dexamethasone by one dosing	Grade 0-2, then resume dex at next
	level without holding dose	lower dosing level.
Myopathy	For Grade 2-4, decrease dexamethasone by one dosing level without	
	holding dose	
Hyperglycemia	For Grade 2, add oral	Add oral hypoglycemic agents and/or
	hypoglycemic agents and/or	Insulin, and decrease dosing level by
	insulin to control blood sugar. If	one.
	hyperglycemia not able to be	
	easily controlled, decrease	
	dexamethasone by one dosing	
	level without holding dose.	
Other	For Grade 2, decrease	Hold dex until severity decreases to
	dexamethasone by one dosing	Grade 0-2, then resume dex at next
	level without holding dose	lower
	_	

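### Section 5.5.1 and Table 3 give opposite Cycle 1 pomalidomide orders for two early sub-DLT cytopenias, and for restart after an early venous-thrombosis DLT

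*Combined protocol and SAP*

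**What the plan says.** Section 5.5.1 sets a Cycle 1 rule: "Unless a DLT is documented to have occurred, no dose modification is allowed during Cycle 1". It adds that when treatment resumes after a Cycle 1 DLT, pomalidomide must come down one level.

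Sections 5.4.2 and 10.2 define a DLT as a first-cycle event: "toxicity considered by the investigator to be related to Pomalidomide; Grade 4 thrombocytopenia or neutropenia", or non-hematologic toxicity of Grade 3 or higher.

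Table 3, in Section 5.5.4, governs changes within a cycle and makes no exception for Cycle 1. Its neutropenia row covers Grade 3 with fever as well as Grade 4. For onset on Days 2-14 it says: "If neutropenia has resolved to ≤ grade 2 prior to Day 21, restart pomalidomide at next lower dose level and continue the cycle". Its platelet row starts at Grade 3 (below 50,000/mm³) and says: "If thrombocytopenia resolves to ≤ grade 2 prior to Day 21, restart pomalidomide at next lower dose level and continue the cycle". For venous thrombosis or embolism of Grade 3 or higher with onset on Days 2-14, it calls for a hold, anticoagulation, and a restart at the investigator's discretion at the same dose.

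Section 5.5.2 sends staff to the tables without any Cycle 1 limit: "Dosing will be adjusted as needed by study investigators as outlined in the tables in Section 5.5.3". Section 5.6.2 prohibits G-CSF in Phase I Cycle 1. Section 10.3 analyzes subjects for the MTD by the dose they actually received.

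**The concern.** Two operative dosing rules apply to the same subject in the same cycle and give different answers. Staff who see Grade 3 thrombocytopenia on Day 8 of Cycle 1 have one text ordering a lower-dose restart after recovery and another forbidding it. If they follow Section 5.5.1 literally, the subject goes back to full dose after a platelet count below 50,000/mm³. If they follow Table 3, they breach the Cycle 1 bar.

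The conflict falls inside the window on which the MTD rests. A subject reduced in mid-cycle finishes the DLT assessment below the cohort's dose, and Section 10.3 does not say at which level that subject counts.

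**Working it through.** This is a comparison of texts. The contradiction itself involves no arithmetic.

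**Event by event, Cycle 1, pomalidomide-related**

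| Event | DLT? | Section 5.5.1 | Table 3 and Section 5.5.3 | Conflict? |
|---|---|---|---|---|
| Grade 3 thrombocytopenia, onset Days 2-14, recovers before Day 21 | No (Grade 4 needed) | No dose change | Restart one level lower | Yes |
| Grade 3 neutropenia with fever, same timing | No (Grade 4 needed) | No dose change | Restart one level lower, or keep the dose with G-CSF | Yes in Phase I, where Section 5.6.2 removes the G-CSF route |
| Either cytopenia, onset Day 15 or later | No | No dose change in Cycle 1 | Omit for the rest of the cycle; reduce in Cycle 2 | No, if a hold is not a modification |
| Venous thrombosis Grade 3 or higher, onset Days 2-14 | Yes (non-hematologic) | Restart one level lower | Restart at the same dose | Yes |
| Venous thrombosis Grade 3 or higher, onset Day 15 or later | Yes | Restart one level lower | Omit; Section 5.5.3 then starts the new cycle one level lower | No |

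Two classifications support the table. Grade 3 neutropenia with fever is read as hematologic, because the DLT definition names only Grade 4 neutropenia and Table 3 keeps neutropenia apart from its row for other non-hematologic toxicity. Venous thrombosis is read as non-hematologic. The thrombocytopenia row needs neither reading.

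**Which text prevails?** None says. Section 5.5.2 directs staff to the tables with no Cycle 1 limit. It cites Section 5.5.3, a number used twice, although Table 3 sits under Section 5.5.4.

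**How often.** The documents give no rate for an attributable Grade 3 event in Cycle 1 with onset on Days 2-14 and recovery before Day 21. The nearest figure is in Section 3.2: Grade 3 or 4 thrombocytopenia in 2 of 60 myeloma subjects at 2 mg, or 3.3% (exact 95% CI 0.4% to 11.5%). It includes Grade 4 and is not confined to Cycle 1, so it is broader than the trigger. It also comes from a different disease and the lowest planned starting dose. The rate r is therefore an assumption. With six subjects, the most planned at one escalation level, the chance of at least one case is 1 - (1 - r)^6:

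- r = 1%: 1 - 0.99^6 = 0.059
- r = 2/60: 1 - (58/60)^6 = 0.184
- r = 5%: 1 - 0.95^6 = 0.265

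Neutropenia with fever would add to this; no rate for it is given.

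**The case against.** The strongest reply is that Section 5.5.1 is the specific Cycle 1 rule, set in a passage on DLT assessment, while Table 3 is general, so Section 5.5.1 governs Cycle 1. That is a reasonable inference, and the same context suggests that the bar is aimed at the DLT-evaluation phase, although its wording is not limited to Phase I. But no clause states this precedence, and each rule is specific in its own way: one by cycle, the other by event. The inferred reading would also restart full dose after Grade 3 thrombocytopenia.

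A second reply is that the trigger is narrow. This stands. With Cycle 1 counts scheduled on Days 8, 15 and 22, it essentially means an abnormal count on Day 8 that has recovered by Day 15.

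A third is that letting Table 3 operate weakens the exposure protection that the Cycle 1 bar provides, and that a Cycle 1 footnote to Table 3 would also remove the contradiction. Both are true. The footnote would, however, fix the full-dose restart in writing.

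A reader might infer more than the documents support:

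- *That holds are barred, so dosing continues through the event.* The Section 5.5 heading, "Dose Continuation, Modification and Interruption", and the Section 5.5.4 heading both treat interruption as distinct from modification, and Section 5.7 lets the investigator stop treatment for harm. Holds are not clearly barred.
- *That dexamethasone reductions clash too.* Table 4, under "Dose Modifications for Dexamethasone", does reduce for sub-DLT events; its myopathy row begins "For Grade 2-4, decrease dexamethasone by one dosing level without". But DLTs must be pomalidomide-related, and the assigned regimen is already 10-20 mg, so the first step from 20 to 10 mg stays within it.

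**Conclusion.** The conflict is real for three situations: Grade 3 thrombocytopenia and Grade 3 neutropenia with fever, each with onset on Days 2-14 of Cycle 1 and recovery before Day 21, and restart after a venous-thrombosis DLT with onset on Days 2-14. In each, one of the two written orders has to give way. It should be fixed, because it concerns the dose given after a serious toxicity and a few sentences resolve it.

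The 6% to 26% range for six subjects at one level rests on assumed thrombocytopenia rates of 1% to 5%. The contradiction stands at any rate.

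A reader might go on to infer that the MTD would come out wrong. The documents do not show that. If a reduced subject is kept at the starting level, that subject simply counts there. If the subject is not counted there, Section 5.4.2 still requires at least three subjects per dose group, so the likely result is one more enrollment. The gap is a missing counting rule. Nor should the frequency be scaled to every possible Phase I subject: the schedule footnote suggests that cohorts 1 and 2 have already been treated, and an amendment cannot reach them.

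**What to change.** 1. Amend Section 5.5.1 along these lines: *In Cycle 1 the pomalidomide dose may be changed only if a DLT occurs or Table 3 requires a hold, reduction or discontinuation.* Correct the table reference in Section 5.5.2 to Section 5.5.4.
2. State that the one-level reduction in Section 5.5.1 governs restart after a Cycle 1 venous-thrombosis DLT, which matches what already happens for late onset, and align the Table 3 cell. If the sponsor prefers to keep the dose, write that exception into Section 5.5.1.
3. State in Section 10.3 that a subject reduced within Cycle 1 stays assigned to the starting dose level for the MTD. List these sub-DLT reductions beside the DLT count at each cohort decision.

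The cost is a minor wording amendment with no new assessments and no change to the DLT definition. The downside is slightly lower Cycle 1 exposure at the assigned level for the few subjects affected. Because they would count as DLT-free at that level if no DLT follows, this could mildly favor escalation. The listing in step 3 lets the investigators see and weigh it.
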